**Table 1: Schedule of Treatments and Assessments**

Required Assessments	Screening			Procedure		Post-procedure follow up								
	SV1	2Wk	SV2	Procedure	DC	2Wk	1M	6Wk	8Wk	10Wk	3M	4M	6M	12M
Mode (O- in office, P-phone)	O	O	O			O	O	P 	P 	P 	O	O	O	O
Window (M-month, Wk-week, d-days)	--	±3 d			--	±3 d	±7 d	±3 d	±7 d	±3 d	±14 d	±7 d	±14 d	±30 d
Medical history	X													
Clinical assessment		X	X			X	X				X	X 	X 	X 
Renal denervation procedure				X										
OBP per study guidelines	X	X	X		X	X	X	X 	X 	X 	X	X	X	X
24h ABPM per study guidelines			X								X		X	X
Witnessed pill intake 													X	X
Medications prescribed 												X 		
Blood tests (Chem7) 			X		X		X				X		X	X
Serum or urine pregnancy test			X											
Drug testing			X								X			
Renal artery imaging- angiogram				X										
Renal artery imaging-DUS 													X	
Mortality assessment 						X	X	X	X	X	X	X	X	X
Medication and event review	X	X	X	X	X	X	X	X	X	X	X	X	X	X 

1: 4M follow-up is only required if 3M systolic OBP≥140 mmHg, prescribe AH medications according to **section 9.1.9** if SBP ≥ 140 mmHg

2: If medically necessary, phone contact may be replaced with office visit. OBP (per **Appendix 16.5**) to be obtained for an office visit or following alternative methods of data collection as described in **section 9.1.6**.

3: Witnessed pill intake (if subject is taking AH medications), complete after OBP measurements

4: Bicarbonate will not be measured for subjects enrolled in Europe.

5: DUS required as first line imaging modality at 6M. Repeat DUS, MRA, CT or angiogram to be used if DUS is nondiagnostic. Renal angiography must be used if repeat DUS/CTA/MRA is nondiagnostic or stenosis >60-70% is suspected. If renal imaging is not captured at the 6M follow-up visit due to extenuating circumstances, renal imaging is required at the next scheduled study visit.

6: Mortality assessment will be completed by the investigational site when a subject cannot be reached after each of the protocol required follow-up visits

7: SAE only review required at 12M visit

8: Clinical assessment of weight only

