#### 4.2.2. *Safety endpoints*

- Composite safety endpoint at 1, 3, 6, and 12 months post-procedure:  
Incidence of the following events:
  - All-cause mortality
  - End-stage renal disease (ESRD)
  - Significant embolic event resulting in end-organ damage
  - Renal artery perforation requiring intervention
  - Renal artery dissection requiring intervention
  - Vascular complications

- Hospitalization for hypertensive crisis not related to confirmed non-adherence with medications or the protocol
- New renal artery stenosis > 70%, confirmed by angiography and as determined by the angiographic core lab at 6-months follow up
- Myocardial infarction
- Stroke
- Renal artery re-intervention
- Major bleeding according to TIMI definition (i.e., intracranial hemorrhage,  $\geq 5$  g/dl decrease in hemoglobin concentration, a  $\geq 15\%$  absolute decrease in hematocrit, or death due to bleeding within seven days of the procedure)
- Increase in serum creatinine  $> 50\%$  from Screening Visit 2

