## 5. Study Design

The SPYRAL DYSTAL study is a multi-center, international, prospective, interventional, single-arm study designed to study renal denervation in the distal portion of the main renal arteries and first-order branches. Denervation will be performed using the Symplicity Spyral multi-electrode renal denervation catheter (Symplicity Spyral catheter) and the Symplicity G3 renal denervation radio frequency (RF) generator in a hypertensive population. Subjects will be studied to assess the impact of this renal denervation approach on systolic and diastolic blood pressure.

The Symplicity Spyral catheter and Symplicity G3 generator provide a spiral pattern of denervation, ensuring circumferential nerve ablation, which is expected to minimize procedure variability. One Symplicity G3 generator is intended to be used with a Symplicity Spyral catheter in enrolled subjects. Subjects will be studied in the absence of anti-hypertensive medications through the 3-month visit to assess the impact of renal denervation on blood pressure in the absence of medications.

Based on previous experience with the SPYRAL HTN-OFF MED study, it is anticipated that there will be subjects who will no longer meet study eligibility during the screening period; therefore, approximately 350 subjects will be enrolled to ensure approximately 50 hypertensive subjects will undergo the renal denervation procedure at up to 15 sites. Once enrolled, subjects will undergo screening visits and if eligible, will undergo renal denervation and will be followed for at minimum 12 months post-procedure. Follow-up visits will take place at discharge, 2Wk, 1M, 6Wk, 8Wk, 10Wk, 3, 4 (if applicable), 6, and 12 months (see **Table 1** for treatments and assessments that will occur at each visit). Upon completion of all follow-up visits, subjects will be exited from the study. Subjects will be consented for a maximum follow-up of 5 years in case there are reasons that would require the follow up to be extended beyond the currently planned 12-months follow up.

The following procedures are defined as outside of Standard of Care CIP procedure (applicable as of EU MDR Date of Application) any time they are conducted as per the schedule of events outlined in the CIP:

- Study requirement for subjects to be off antihypertensive medication until the 3-month visit.
- Medication re-introduction
- Office Blood Pressure
- 24-hour Ambulatory Blood Pressure Monitoring (ABPM), except in several EU countries

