- **Renal artery imaging** will be performed at the 6-month follow-up visit to assess if a renal artery stenosis is suspected. A renal duplex ultrasound (DUS) will be obtained at 6-months follow up and submitted to the DUS Core Laboratory. If the DUS is determined to be nondiagnostic a repeat DUS, a MRA, CT or angiogram will be performed (repeat imaging is to be completed within 30 days after confirmation of non-diagnostic imaging). If evidence of a clinically significant stenosis is indicated by the DUS or MRA/CT Core Laboratory, an angiogram must be obtained and submitted to the angiographic core laboratory.
  - If renal imaging is not obtained at the 6-month follow-up visit due to extenuating circumstances, renal imaging is required at the next scheduled study visit.
- **24-hour ABPM** will be conducted at the 3, 6, and 12-month follow-up visits post-procedure according to the guidelines in **Appendix 16.5**. A repeat ABPM will be required in the event of technical issues, failure to follow ABPM guidelines or if the minimum required number of daytime and nighttime readings is not obtained. If ABPM is repeated office blood pressure and drug testing (for 3-month follow up only) must be repeated on day the ABPM is applied.
  - Initiate medication re-Introduction for subjects with systolic OBP  $\geq 140$  mmHg at 3-month follow-up visit. Starting at the 3-month follow up after clinical assessment and a valid ABPM are completed.
- **Mortality assessment** will be completed by the investigational site when a subject cannot be reached after each of the protocol required follow-up visits.
- **Drug testing** (urine/blood) to ensure medications are no longer present in the subject's system. A urine sample will be collected, preferably using the subject's first morning urine. A blood sample will be collected at the time of the visit. Drug testing samples collected for subjects that screen fail after obtaining the sample, must not be sent to the core lab for analysis.

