### ***9.1.8. Confirmatory Blood Draws to Assess Renal Function***

Serum creatinine values will be assessed throughout the study. A second blood draw will be required to confirm a sustained change in renal function in the event of one of the following:

- >50% increase in serum creatinine from baseline (Screening Visit 2)
- eGFR <15 mL/min/1.73m^2 using the 4 variable MDRD calculation

The additional blood draw must be taken at least 21 days from the date of the event noted above and documented on an Unscheduled Follow-up CRF. In the event the second blood draw results in the same event (e.g., >50% increase in serum creatinine from baseline), an adverse event must be reported. If the event is a continuation of an already-identified sustained elevation that did not return to <50% of baseline value, another blood draw is not necessary.

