### ***11.2.1. Reporting Process***

All adverse events, regardless of relatedness or outcome, must be recorded and reported through the 6-month follow up. After the 6-month visit has been completed, only serious adverse events (SAEs) are required to be recorded and reported. Adverse events will be documented on the appropriate CRF, reported by the investigational site to Medtronic, and to the EC/IRB (if required) within the EC/IRB required timeframe and local and national regulations, as applicable. Adverse events shall be reported on the adverse event CRF, one CRF for each adverse event term. The site should make all effort to provide the information required on the Adverse Event CRF and all adverse events should be reported within the event reporting timeframe requirements (refer to **Section 1.1.1**). For adverse events that require immediate reporting, initial reporting will be done on the CRF by completing as much information as is available. The AE CRF must be "saved as Complete" in the remote data capture (RDC) system to ensure it is reported to Medtronic as soon as possible. For any changes in status of a previously reported adverse event or DD (i.e. change in actions taken, change in outcome, change in relatedness), information needs to be updated on, or added to the original AE or DD form.

All adverse events and device deficiencies will be reviewed by the Medtronic Core Clinical Solutions Safety Department. This review will include the determination whether the adverse event meets regulatory reporting requirements. The sponsor will ensure timely adverse event/device deficiency reporting to meet global regulatory requirements. In case the adverse event/device deficiency is related to a Medtronic market released device used during the study, the Medtronic employee who first becomes aware will report this device related adverse event/device deficiency to the Medtronic Product Experience

Management (PXM) within 48 hour timeframe.. The Medtronic Product Experience Management (PXM) will ensure prompt review and appropriate reporting.

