Appropriate cardiac enzyme data (respecting top-down hierarchy):

a) CK greater than or equal to 2\* URL confirmed by:

- CKMB > 1\*URL or
- in the absence of CKMB: Troponin > 1\*URL or

b) in the absence of CK:

- CKMB > 3\*URL
- In the absence of CK and CKMB: Troponin > 3\*URL
- In the absence of CK, CKMB and Troponin, clinical decision based upon clinical scenario

**New renal artery stenosis:** Greater than 70% renal artery stenosis confirmed by analysis of angiography by the core lab. If core lab analyses are unavailable, site reported analysis may be used. The date of the event will be the date of confirmatory angiography.

**Renal artery dissection:** Creation of a false lumen between the layers of the artery requiring intervention.

**Renal artery perforation:** Puncture creating a hole in the vessel wall requiring intervention.

**Renal artery reintervention:** Interventional procedure performed on the renal artery following completion of the renal denervation procedure and removal of the guide catheter.

**Significant embolic event:** Sudden obstruction of a blood vessel by debris (i.e., blood clot, plaques, fat, bacterial mass, cancer cells, or air bubbles) resulting in end-organ damage. Examples include:

- Kidney/bowel Infarct: necrosis (cell death) of an area of tissue in all or part of the organ due to cessation of the blood supply due to stenosis or occlusion
- Lower extremity ulceration: a non-healing lesion on a body surface (i.e., skin, mucous membrane)
- Gangrene: necrosis of tissue usually resulting from deficient or absent blood supply
- Doubling of serum creatinine confirmed by at least two measurements over 21 days apart
- DOES NOT INCLUDE MI OR STROKE WHICH ARE ADJUDICATED SEPARATELY

**Stroke:** Sudden onset of vertigo, numbness, dysphasia, weakness, visual field defects, dysarthria, or other focal neurological deficits due to vascular defects in the brain such as hemorrhage, embolism, thrombosis, or rupturing aneurysm, that persists more than 24 hours.

**Vascular Complications:** Complications that require surgical repair, interventional procedure (not including manual compression), thrombin injection, or blood transfusion (requiring more than 2 units of packed red blood cells within any 24-hour period during the first 7 days post-procedure); possible vascular complications are as follows:

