7.7. Evaluation of Objectives

7.7.1. Safety Objectives

The following safety endpoints will be evaluated:

- Major Adverse Events (MAE), defined as a composite of the following event at 1 month post-procedure (6 months for renal artery stenosis):
 - All-cause mortality
 - End-stage renal disease (ESRD)
 - Significant embolic event resulting in end-organ damage
 - Renal artery perforation requiring intervention
 - Renal artery dissection requiring intervention
 - Vascular complications
 - Hospitalization for hypertensive crisis not related to confirmed non-adherence with medications or the protocol
 - New renal artery stenosis >70%, confirmed by angiography and as determined by the angiographic core lab at 6 months follow-up
- Composite safety endpoint, defined as a composite of the following event at 3, 6 and 12-month post-procedure:
 - All-cause mortality
 - End-stage renal disease (ESRD)
 - Significant embolic event resulting in end-organ damage
 - Renal artery perforation requiring intervention
 - Renal artery dissection requiring intervention
 - Vascular complications
 - Hospitalization for hypertensive crisis not related to confirmed non-adherence with medications or the protocol

This document is electronically controlled. Printed copies are considered uncontrolled.

Confidential

- New renal artery stenosis >70%, (For the composite safety endpoint at 3 and 6 months, use RAS at 6 months, which confirmed by angiography and as determined by the angiographic core lab at 6 months follow-up. For the composite safety endpoint at 12 months use RAS available at 12 months)
- Myocardial infarction
- Stroke
- Renal artery re-intervention
- Major bleeding according to TIMI definition (i.e. intracranial hemorrhage, $\geq 5\text{g/dl}$ decrease in hemoglobin concentration a $\geq 15\%$ absolute decrease in hematocrit, or death due to bleeding within 7 days of the procedure)
- Increase in serum creatinine $>50\%$ from SV2 (not CEC adjudicated)

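### Only serious events must be reported after the 6-month visit, but the 12-month safety endpoints include stenosis and creatinine events that need not be serious, and nothing exempts endpoint events from that limit

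*Protocol*

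**What the plan says.** **Collection.** All adverse events are collected up to 6 months. From then on the rule in Protocol 11.2.1 is: "After the 6-month visit has been completed, only serious adverse events (SAEs) are required to be recorded and reported". Sections 9.1.6, 9.2 and 11.2 say the same. Table 1 footnote 7 adds "SAE only review required at 12M visit", and the same note is footnote 7 in Table 3 and footnote 3 in Tables 2 and 4.

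**Endpoints.** Protocol 4.2.2 defines the "Composite safety endpoint at 1, 3, 6, and 12 months post-procedure", with new renal artery stenosis above 70% as a component, and lists a creatinine rise above 50% from Screening Visit 2 among the safety endpoints. For stenosis, SAP 7.7.1 instructs: "For the composite safety endpoint at 12 months use RAS available at 12 months".

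**Stenosis.** Imaging is scheduled at the 6-month visit only. If it is missed, "renal imaging is required at the next scheduled study visit" (9.1.6). Under 16.4, "The date of the event will be the date of confirmatory angiography".

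**Creatinine.** Section 9.1.8 covers the whole study. It asks for a second draw at least 21 days after a rise above 50% and says that, if the rise is confirmed, "an adverse event must be reported".

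**Exit.** Protocol 5 states: "Upon completion of all follow-up visits, subjects will be exited from the study".

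**Counting.** SAP 7.7.1 builds the numerator from CEC-adjudicated events and exempts creatinine from adjudication. Protocol 13.5 has every safety endpoint adjudicated.

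**The concern.** What a site must report and what the analysis must count diverge after the 6-month visit. Whether a stenosis enters the 12-month composite could then turn on a site's judgement of seriousness, although the endpoint definition has no such condition. Protocol 10.1 names renal artery stenosis as a possible consequence of the procedure or of the RF energy, and treatment of the first-order branches is the technique under study. If non-serious endpoint events are lost between 6 and 12 months, the 12-month rates are too low. They are also not comparable with the 1-, 3- and 6-month rates, which rest on collection of all adverse events.

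**Working it through.** Most of this check sets sections side by side. Arithmetic applies to the confirmation window and to the weight of one missed event.

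1. **Can an endpoint event be non-serious?** Neither endpoint definition (4.2.2, 16.4) asks for seriousness. The SAE definition in 11.1 covers death, life-threatening illness, permanent impairment, hospitalization, and intervention to prevent such harm. A stenosis that is treated would often qualify. An untreated, asymptomatic one, or a laboratory rise alone, need not. Note 1 to that definition also removes admissions for procedures the protocol requires, and 9.1.6 makes the angiogram mandatory once the core lab sees a clinically significant stenosis.

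2. **When is a stenosis dated?** The sequence in 9.1.6 is ultrasound at the 6-month visit, core-lab reading, repeat imaging within 30 days if the first is non-diagnostic, then angiography. The event takes the angiogram's date, so it can fall after the 6-month visit. Deferred imaging falls at 12 months. The documents give no typical delay, so the share of stenoses dated in the SAE-only period cannot be stated.

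3. **How does a stenosis reach the numerator?** Only through CEC adjudication (SAP 7.7.1). Protocol imaging goes to the core labs (9.1.6), but neither document says that a core-lab reading opens a CEC case without a site event form. A stenosis found after 6 months outside protocol imaging lacks even the core-lab route. Section 16.4 would accept a site reading where the core lab's is unavailable, but the site is not obliged to report a non-serious finding.

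4. **How does a creatinine rise reach the analysis?** Chem-7 is scheduled at 12 months (9.1.6, Tables 1 and 3), and SAP Appendix V selects the 12-month value. The endpoint needs no confirmation and no adjudication under the SAP, so it can be derived from laboratory data. Two gaps remain. Escape subjects move to Table 4 (9.1.9), which schedules no blood tests. And SAP 7.7.1 gives a numerator rule only for adjudicated events, so creatinine has none.

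5. **Can a 12-month rise be confirmed?**
   - The SAP window reproduces: 360 - 30 = 330 and 360 + 30 = 390.
   - The latest draw that can be confirmed by day 390 is 390 - 21 = day 369.
   - Days 330 to 369 are 369 - 330 + 1 = 40 of the 390 - 330 + 1 = 61 window days.
   - A draw on target day 360 can be confirmed from 360 + 21 = day 381.
   - A draw on day 390 can be confirmed from 390 + 21 = day 411, outside the protocol window but inside the SAP's expanded window, which ends on day 540.

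   Confirmation is therefore feasible. However, no visit is scheduled for it and no text holds exit open. Confirmation also matters beyond the event form: 16.4 requires two eGFR values at least 21 days apart for end-stage renal disease, and repeat measurements for the creatinine-doubling example of an embolic event.

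6. **Weight of one event** (exact Clopper-Pearson limits; evaluable n is an assumption). For x = 1 the lower limit is 1 - 0.975^(1/n). For x = 0 the upper limit is 1 - 0.025^(1/n).

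| Evaluable n | Event counted | Event missed |
|---|---|---|
| 50 | 1/50 = 2.0% (0.05-10.6%) | 0/50 = 0% (0-7.1%) |
| 40 | 1/40 = 2.5% (0.06-13.2%) | 0/40 = 0% (0-8.8%) |

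**The case against.** The best defence is that both endpoints have routes that do not depend on event reporting. Creatinine comes from a scheduled blood test, and the SAP does not adjudicate it. Stenosis on protocol imaging, including imaging deferred to 12 months, goes to the core labs whatever the site thinks of its seriousness, and the endpoint is defined by the core-lab reading. The CEC works under a separate charter that may provide for direct referral. Most other composite components are serious by nature. The SAE-only rule is also a declared choice: Protocol 7.1 ties it to the pre-market focus of the ISO 14155 adverse event requirements.

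Much of this stands, and it rules out three readings that a reader might infer:

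- *A 12-month creatinine rise cannot be confirmed before exit.* Section 9.1.7 provides unscheduled visits for repeat creatinine draws, 9.6.1 encourages subjects to stay until results are received, consent allows follow-up to 5 years, and 40 of the 61 window days leave room for the second draw. Confirmation is possible but not assured.
- *Creatinine events after 6 months are lost.* For subjects who have not escaped, the endpoint value is captured. What may be missing is the adverse event record.
- *Most stenoses found by the 6-month imaging go uncounted.* The documents state no delay to angiography, and the images do reach the core lab.

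The defence does not close the gap. Neither document links the core lab to the CEC without a site report, a stenosis found outside protocol imaging has no other route, and Table 4 has no blood tests. The rationale in 7.1 explains why general adverse event collection narrows. It does not address how the 12-month endpoints are to be captured.

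**Conclusion.** The conflict is real and limited. After the 6-month visit the reporting rule is narrower than the endpoint definitions, with no exemption for endpoint events. The exposure is clearest for a non-serious stenosis found outside protocol imaging. It is less certain for one found by protocol imaging, where the missing step is the referral from core lab to CEC. For creatinine, 9.1.8 and 11.2.1 contradict each other on reporting after 6 months, escape subjects may have no 12-month value, and the SAP lacks a counting rule.

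Any bias in the 12-month rates would be downward, but its size cannot be derived from the documents. The one-event illustration shows only how much a single case weighs at this sample size, assuming 40 to 50 evaluable subjects. The conclusion assumes that the CEC charter, which is not part of these documents, does not already supply the missing route. The safety analysis is descriptive with no comparator, so no formal test is affected. The correction is still worth making because it is cheap.

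**What to change.** - **Protocol 9.1.6, 9.2, 11.2, 11.2.1, footnote 7 of Tables 1 and 3, and footnote 3 of Tables 2 and 4:** change the rule after 6 months to all SAEs plus any event that meets a safety endpoint definition in 4.2.2 or 16.4, regardless of seriousness.
- **Protocol 9.1.6 or 12.1:** state that a core-lab stenosis above 70% goes to the CEC without needing a site SAE report.
- **Protocol 9.1.8 and 11.2.1:** reconcile the two, and state that study exit waits for the confirmatory draw that 9.1.8 already requires.
- **SAP 7.7.1:** give the data source and numerator for the non-adjudicated creatinine endpoint, say how escape subjects without a 12-month value are handled, and align Protocol 13.5 with the exemption from adjudication.

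The cost is wording, a CRF instruction, a few extra event forms, and an occasional exit delayed by about 3 weeks. Existing consent already allows follow-up beyond 12 months.
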